#### **Statistical Analysis:**

Continuous variables will be expressed as mean and standard deviation or median and interquartile range (25th-75th percentiles) where appropriate. *Student's paired t test or the Wilcoxon signed rank test* and One-way repeated measures ANOVA or the Friedman test will be used for comparison as appropriate. The within-subject variance-covariance matrix will be evaluated by the compound symmetry method. Categorical variables will be presented as frequency or percentage. Fisher's exact test will be used for comparison at each glucose level. Cochran's Q test will be used for comparison of proportions. A two-tailed  $p$ -value  $<0.05$  will be considered statistically significant. Statistical analysis will be performed using SPSS (version 15.0.0, SPSS Inc.) and SAS version 8.2 (SAS Institute, Cary, NC).

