**Objectives:**

1. To monitor blood sugar and cardiac function continuously for 6 days.
2. To determine if there is a correlation between hypoglycemia and alterations in cardiac rhythm, alterations in cardiovascular autonomic function and myocardial ischemia.
3. To collect baseline data to design a subsequent study to assess the effects of various interventions designed to protect the cardiovascular system against hypoglycemia if objectives 1 and 2 are achieved.

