awareness of warning symptoms, and altered psychomotor performance. Indeed, recent data suggest that asymptomatic hypoglycemia is shockingly common in these patients. When assessed by continuous glucose monitoring, 65% of elderly diabetic patients have frequent hypoglycemic episodes lasting up to an hour that are entirely asymptomatic (Munshi, [name]). The consequences of frequent, severe and/or asymptomatic hypoglycemia in this patient population have not been clearly defined. The risk of hospitalization and death is detailed above, but this is probably a "tip of the iceberg" phenomenon since hypoglycemia is so frequently asymptomatic in this age group. It is known that severe hypoglycemia increases the risk of dementia ([name]). Older patients on insulin have an increased frequency of falls and fractures, and this is more likely as the HgbA1C falls, implying that low blood sugars may be a contributing factor ([name]). Elderly patients with diabetes have an increased frequency of syncope, cardiac arrhythmias, myocardial infarction, and sudden death and the risk of these events is more than doubled in patients treated with agents that are known to cause hypoglycemia (Currie). However, other than some anecdotal reports of low blood sugars at the time of these events, no studies have carefully evaluated the relationship between hypoglycemia and cardiac function in this age group. In this study we propose to evaluate the association between hypoglycemia, as measured by continuous glucose monitoring, and cardiac rhythm, cardiovascular autonomic function and myocardial ischemia, as measured by continuous electrocardiographic (ECG) monitoring.

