This is a feasibility pilot to establish preliminary data for analysis. The CardioSTAT monitor will allow assessment of cardiac arrhythmias, myocardial ischemia and cardiovascular autonomic function. The results from the glucose sensor and the CardioSTAT monitor will be correlated and compared to each other to determine if hypoglycemia has an adverse effect on heart function. Hypoglycemia is likely to induce autonomic responses captured on the CardioSTAT and concordant ischemic ST changes if coronary disease is present. It may also detect any resultant arrhythmias, although ischemic arrhythmias are

uncommon in 6 days of monitoring. If we determine that hypoglycemia has negative effects on cardiac function, we may be able to design treatments that would prevent these effects from happening in the future.

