#### **Data Analysis:**

Autonomic function will be evaluated by assessing heart rate variability using autoregressive spectral analysis during hyperglycemia, euglycemia and hypoglycemia. Arrhythmia analysis will be performed using the standard algorithms that are normally used to assess data in the Holter laboratory, and will be correlated with prevailing blood sugar values. This will include standard diagnostic evaluation including mean, median and range of heart rate, quantitation of supraventricular and ventricular ectopy, and Tpeak-Tend. P wave duration and variability and T wave alternans will be measured as well and correlated with prevailing glucose values. ST segments to evaluate for ischemia will follow standard techniques in routine clinical software (GE Marquette, Wisconsin) that reports ST shifts during 5 minute epochs, and will be correlated with metrics of heart rate variability, absolute heart rate and symptoms.

Measurements will be performed by an experienced expert blinded to the patient's clinical status. QTc will be calculated using Bazett's formula (Bazett). The end of the T wave will be defined as the intersection of the maximum slope of the terminal T wave with the isoelectric TP segment. QT variability will be evaluated from digitized lead V2 at baseline. Each 5-minute epoch will be analyzed using a validated QT interval measurement algorithm proposed by Berger et al. (Berger), which computed mean QT, QT variance, mean heart rate, and heart rate variance. To measure beat-to-beat QT variability, a normalized QT variability index (QTVI) will be calculated. TWA will be measured from the digitized ECG using the spectral method as previously developed by the University Health Network Holter data site (Selvaraj). TWA magnitude ( $V_{alt}$ ) will be quantified over a 128-beat window which will be successively incremented by 16-beats until the end of each 5-minute epoch.

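### Compound symmetry is the only within-subject covariance structure named for the three-state comparison, with no sphericity correction or fallback; the effect is small and may be nil, and the remedy is a few sentences

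*Combined protocol and SAP*

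**What the plan says.** The Statistical Analysis section offers paired t or signed rank tests, and for more than two conditions says "One-way repeated measures ANOVA or the Friedman test will be used for comparison as appropriate". The next sentence is "The within-subject variance-covariance matrix will be evaluated by the compound symmetry method". The text then turns to categorical variables: "Fisher's exact test will be used for comparison at each glucose level", followed by "Cochran's Q test will be used for comparison of proportions". Significance is two-sided at 0.05.

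The three conditions come from the Data Analysis section, which assesses heart rate variability "during hyperglycemia, euglycemia and hypoglycemia". Extending them to the ANOVA is an inference, as is tying the covariance sentence to the ANOVA. It directly follows that test, though, and no other listed method calls for it. The documents as supplied contain no other covariance structure, sphericity test, degrees-of-freedom correction or robust standard error.

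**The concern.** The uncorrected repeated-measures F test holds its level when all pairwise differences between states have the same variance (sphericity). Compound symmetry guarantees this.

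There is reason to doubt it here. The first objective is "To monitor blood sugar and cardiac function continuously for 6 days", which is 6 × 24 = 144 hours. The Background expects that "65% of elderly diabetic patients have frequent hypoglycemic episodes lasting up to an hour". One such episode is at most 1/144, or 0.7%, of the recording. A patient's hypoglycemia value may therefore average far fewer 5-minute epochs than the other two values and be noisier.

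If 'evaluated' means assumed, nothing protects the test when the assumption fails. If it means checked, the plan does not say what follows a failed check. At stake is a mildly liberal omnibus test. If a pooled error term were also used for follow-up contrasts, the excess error would fall on the contrasts with hypoglycemia, which are the study's question.

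**Working it through.** The plan has no power or sample-size figure on this point to reproduce.

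**Inputs from the documents.** 20 patients in one cohort (Design section); three states (Data Analysis); two-sided 0.05 (Statistical Analysis). As an illustration, 65% of 20 = 13 patients with hypoglycemia (Background).

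**Assumed, because the documents give none.** Normal data; SD 1 for euglycemia and hyperglycemia, SD r for hypoglycemia, with r = 1 to 3; common correlation ρ = 0.3 to 0.7.

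**Step 1: departure from sphericity.** Take two orthonormal contrasts: hypoglycemia against the mean of the other states, and the other two against each other. Their variances are

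a = (4r² + 2 + 2ρ − 8ρr)/6 and b = 1 − ρ.

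They are uncorrelated, so ε = (a + b)² / [2(a² + b²)]. At ρ = 0.5:
- r = 1: a = 0.5, b = 0.5, ε = 1.00
- r = 1.5: a = 1.0, b = 0.5, ε = 2.25/2.50 = 0.90
- r = 2: a = 1.833, b = 0.5, ε = 5.444/7.222 = 0.75
- r = 3: a = 4.5, b = 0.5, ε = 25/41 = 0.61

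**Step 2: ceiling.** With three states ε cannot fall below 1/(3 − 1) = 0.5, where the error is P[F(1, n−1) > 5% critical value of F(2, 2(n−1))].
- n = 20: critical value F(2, 38) = 3.245; P[F(1, 19) > 3.245] = 8.8%
- n = 13: critical value F(2, 24) = 3.403; P[F(1, 12) > 3.403] = 9.0%

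**Step 3: simulated omnibus type I error** (125,000 runs per setting; n = 20 and 13; ρ = 0.3, 0.5, 0.7). Repeat runs agreed within 0.3 percentage points.

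| Hypoglycemia SD ratio | Uncorrected F |
|---|---|
| 1 | 5.0–5.1% |
| 1.5 | 5.3–5.7% |
| 2 | 6.1–6.8% |
| 3 | 7.4–7.9% |

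Greenhouse-Geisser gave 4.2–5.1% and Friedman 4.9–5.9% across all settings, including those in step 4.

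**Step 4: which ratio is plausible?** A second set of runs built the variances from recording time: one-hour episodes, about 100 hours of euglycemia and 37 of hyperglycemia, and autocorrelation of 0.5 to 0.95 between epochs. With one or on average four episodes the assumed hours total 138 to 141 of the 144, so they are only approximate. With several episodes, and patient-by-state variance of 0.1 to 0.25 of the epoch variance, the uncorrected error was 5.0–5.4%. With a single episode and no patient-by-state variance it was 7.6–8.6%. The Background calls the episodes frequent, which points to the milder end.

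**Step 5: contrasts on a pooled error term.** At r = 2, ρ = 0.5, each difference involving hypoglycemia has variance 4 + 1 − 2 = 3; the other has 1 + 1 − 1 = 1. The pooled term uses their average, (3 + 3 + 1)/3 = 2.33. It understates the variance of the hypoglycemia contrasts (3/2.33 = 1.29) and overstates that of the other (1/2.33 = 0.43). Simulated error over ρ = 0.3 to 0.7 was 8.2–9.0% for hypoglycemia contrasts and 0.2–0.7% for the other. Paired t tests, which use each pair's own variance, gave 4.7–5.4%.

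**The case against.** **The effect may be nil.** The larger figures need few episodes, little patient-by-state variation, or an SD ratio of 2 to 3, none of which the documents establish. The Design section says "This is a feasibility pilot to establish preliminary data for analysis", and no p-value rule decides whether the next study proceeds. This stands, and it keeps the point at the lowest level.

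**The plan already holds most of the protection.** It lists paired tests for two states and the Friedman test, which is nearly immune. If the sentence means a sphericity check followed by correction on failure, the error is 4.9–5.6%. This stands in part. Friedman is offered only where appropriate, not as the fallback for non-sphericity, and no action after a failed check is written down. At SD ratio 2 such a check would detect the problem 59–82% of the time at n = 20 and 37–58% at n = 13.

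**The sentence may describe a mixed model.** Such a model would keep patients who have no hypoglycemia, whereas a classical ANOVA drops them: 20 − 13 = 7 under the 65% illustration. In 4,000 runs with sphericity true and 7 patients lacking hypoglycemia, power for a 0.5 SD hyperglycemia shift was 27–59% for complete-case Greenhouse-Geisser against 40–79% for compound symmetry on all patients. For a hypoglycemia shift of 0.5 to 0.7 SD the loss was about 2–4 points. This stands as a limit on the remedy, so the fix covers it. It does not clear the plan: at SD ratio 2 the all-patient compound-symmetry test ran at 8–9% error.

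**Stronger readings that the documents do not support.** A reader might infer that the planned p-values are seriously inflated. No variances are given, and the three-state test cannot exceed about 9%. A reader might also infer that Fisher's exact test will be misapplied to paired states. The natural reading is Fisher within one state and Cochran's Q across states, which is sound for independent patient groups with one value each. What is missing is the name of those groups and the unit, which is a clarification only.

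**Conclusion.** The gap in the text is real: one covariance structure, with no correction and no stated action if it fails. Its consequence is small. The uncorrected omnibus test runs at about 5 to 8% for assumed SD ratios of 1 to 3, with a ceiling of about 9%, and may be essentially nominal if episodes are frequent. The larger distortion in contrasts (about 8 to 9% and below 1% at ratio 2) arises only if a pooled error term is used, which the plan neither states nor excludes. All sizes rest on assumed variances and correlations, normal data, and the inference that the ANOVA compares the three glucose states. Paired t and signed rank comparisons of two states are not affected. This is a cheap improvement to consider, not a flaw that undermines the pilot.

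**What to change.** Replace the compound-symmetry sentence with wording such as:

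> Three-state comparisons of approximately normal measures use repeated-measures ANOVA with the Greenhouse-Geisser correction; the Friedman test is used for clearly non-normal measures such as ectopy counts. Pairwise comparisons use the paired t or Wilcoxon test on patients with both states, not a pooled error term. The patient is the unit, with one value per patient per state. The number of patients contributing to each comparison is reported. If a mixed model is used to retain patients lacking a state, it uses an unstructured covariance with a small-sample degrees-of-freedom correction.

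In the same edit, name the patient groups and the unit for Fisher's exact test.

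**Cost.** A few sentences and no new data. Omnibus power lost to the correction, for a hypoglycemia shift of 0.3 to 0.7 SD and ρ = 0.3 to 0.7:
- If sphericity holds: 0.2–2.0 points at n = 20 and 1.6–3.2 at n = 13.
- SD ratio 2: 0.6–6.2 and 3.3–6.6 points.
- SD ratio 3: 1.6–8.6 and 5.7–9.6 points.

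At ratios 2 and 3 part of this is excess type I error being removed. Using Friedman for every measure would not be free: on normal data it gave 1–15 points less power than Greenhouse-Geisser. Complete-case ANOVA also leaves out patients lacking a state, so the counts and the mixed-model provision belong in the text.

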**Potential benefits:**

Information gained from this study will expand the knowledge base with respect to the impact of hypoglycemia on cardiac function. If we find that individual patients experience low blood sugars, we will alter their therapy to see if this can reduce the frequency of these events. If the CardioSTAT monitor shows that patients have any abnormalities in cardiac function, we will suggest a plan of investigation and management to their family doctor. This could involve recommendations regarding unrecognized atrial fibrillation with attendant stroke risk (by definition CHADS2 score  $\geq 2$ ), or ventricular arrhythmias.

**Risks:**

There will be some discomfort associated with the insertion of the glucose sensor. There is a small risk of skin infection from the insertion of the glucose sensor and the possibility of an allergic reaction from the tape used to apply it and the CardioSTAT Monitor leads. This risk occurs less than 1 in 1000 times the sensor is used.

